In 2009, an expert panel convened by the Stroke Council of the American Heart Association recommended against routine use of prophylactic anti-epileptic medication for patients with ruptured intracranial aneurysms due to lack of proven benefit [Bederson et al]. Although this group did not make any recommendations regarding the use of prophylactic anti-epileptic drugs during the surgical treatment of unruptured aneurysms, the risk of seizures, and therefore the potential benefits of seizure prophylaxis, appears to be lower in these patients compared with those with ruptured intracranial aneurysms Bederson et al., Baker et al]. Despite a lack of evidence for the use of anti-epileptic medication in preventing seizures in patients undergoing

microsurgical treatment of ruptured and unruptured brain aneurysms, the use of these medications remains common at many institutions including UMHS.

After a thorough review of the existing literature as well as a review of our own practice, the investigators have concluded that the decision to treat patients undergoing aneurysm repair with levetiracetam has reached true clinical equipoise. In other words, we cannot favor a decision to either administer or not administer this drug in these patients based on the existing information. The utility of anti-epileptic prophlaxis in the perioperative period for patients undergoing intracranial aneurysm repair remains a common practice that is not supported by the current literature that includes retrospective analyses as well as prospective trials for similar but not identical types of patients. We propose to settle this dilemma by performing a prospective randomized trial in patients undergoing aneurysm repair in order to definitively determine if the common practice of perioperative antiepileptic drug administration has any utility.

We have chosen to use levitiracetam as the medication for seizure prophylaxis for those patients who will randomize to perioperative seizure prophylaxis. Although phenytoin was the most common drug used for perioperative anti-seizure prophylaxis for many years, it has now been replaced by levetiracetam at many centers because of a perception that it is easier to administer and has fewer side effects [Zachenhofer et al, Milligan et al, Szaflarski et al., Lim et al]. The use of levetiracetam rather than phenytoin will reflect the practice pattern of most centers across the United States.

METHODS

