Timeline: Prospective data for subjects will be collected on a secure file with password access for until up to 10 years after all data is published.

Inclusion/Exclusion criteria:

Inclusion:

- 1. Adult (≥18 years)
- 2. Presence of intracranial aneurysm (with or without rupture)
- 3. Patients with unruptured aneurysms must be recommended for microsurgery. Patients with ruptured aneurysms should be recommended for clipping or coiling.

Exclusion:

- 1. History of seizures within last 10 years
- 2. History of epilepsy
- 3. History of prior stroke
- 4. Currently prescribed medication with anti-epileptic activity (keppra, dilantin, tegretol, lamictal, topamax, etc.)
- 5. Brain tumor
- 6. Pregnant or nursing woman
- 7. Known levetiracetam allergy

Recruitment:

All patients seen at the University of Michigan Health System that meet inclusion criteria are currently seen by one of the investigators for routine clinical care. Prior to surgery, the study

will be explained to potential subjects and/or their legally authorized representatives by an investigator or a qualified study team member and they will be able to ask any questions that they may have. In addition, they may contact the PI (by phone, email, or mail). The investigators will recruit from their own patient population. No additional patient recruitment will be pursued.

Design:

Patients that meet all eligibility criteria will be randomized to either a "levetiracetam" or "no levetiracetam" group. There will be no attempt to "blind" the patient or caregivers with respect to group assignment. The group assignment will be known to the patient as well as relevant caregivers.

Patients in both groups will be treated according to all current reasonable clinical practices for the surgical treatment of intracranial aneurysms and its postoperative care. With the single exception of prophylactic levetiracetam administration to only one group, there will be no differences by design between the two groups with respect to treatment.

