Those assigned to the "levetiracetam" group will receive a 500 mg intravenous dose during the operative case and then will be maintained on 500 mg orally twice a day for a total of seven days. Those patients that are assigned to the "no levetiracetam" group will receive no levetiracetam or any other anti-epileptic medications unless the treating physicians determine that such medications are clinically indicated based on specific circumstances. The use of any anti-epileptic medications will be recorded.

As is typical for all patients undergoing craniotomy for aneurysm repair, patients will be monitored in the neurological intensive care unit for at least one day following surgery. The

patients may then be transferred to a ward room where they will continue to be monitored according to standard clinical practices. If a subject is discharged prior to 7 days, periodic chart review and examination at routine clinical follow ups will be used to determine occurrence of seizure. If a seizure occurs in any patient, the seizure will be treated according to best clinical practices as determined by the treatment team without any regard to the patient's group assignment in the study.

A dataset will be prospectively assembled on each patient included in the study. Recorded information will include patient age, gender, location of aneurysm, size of aneurysm, duration of surgery, surgeon's assessment of degree of brain retraction during surgery (on a 3 point scale: less than average, average, more than average), the surgeon's degree of cortical damage during surgery (on a 3 point scale: less than average, average, more than average), the occurrence of an intraoperative hemorrhage, the occurrence of any other unexpected intraoperative events, the dose of levetiracetam and the duration of administration, any side effects or possible side effects of levetiracetam, the dose and duration of administration of any other anti-epileptic medications, the occurrence of any seizures including the number of such events, their duration, their treatment, and their sequelae if any.

Assessments will occur at routine care follow-up visits. These visits typically occur at 1-2 months, 4-6 months, and 6-12 months and up until 5 years +/- 6 months after surgery. Clinical data collected at these visits, specifically, the incidence of seizures, will be used for the study. Additionally, the study team may follow up on any previously reported adverse events.

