Levetiracetam will not be given to half of the study subjects. Although levetiracetam is often used in these patients for seizure prophylaxis, its utility has never been established. A recent randomized trial found that prophylactic administration of antiepileptic medications in those undergoing routine craniotomy for tumor did not reduce the risk of seizures in that population. Therefore levetiracetam administration should not be considered standard treatment and withholding this medication falls within the scope of reasonable clinical practice.

Levitiracetam is associated with side effects in some cases. A recent trial of levitiracetam prophylaxis found that 1 patient had an adverse drug reaction out of 105 patients that were treated with this drug in the perioperative period [Milligan et al].

As with most anti-epileptic medications, levetiracetam appears to have some teratogenic potential. This potential appears to be dose dependent. All women of child-bearing age will undergo pregnancy testing prior to treatment per UMHS routine care practices. Pregnant women will be excluded from this study and will be treated according to standard practices of the treating physician.

There is a risk of loss of confidentiality. This risk is considered minimal and will be reduced by the maintenance of only de-identified data sets on password protected files.

Benefits: Participating subjects may benefit from increased monitoring by the study team as participants in the trial. Subjects in the levetiracetam group may benefit from reduced incidence of seizure. Subjects in the no levetiracetam group may benefit from a reduced indicence of side effects. Additionally, the study will yield important information to the community of physicians and researchers, and ultimately their patients; thus, there will be benefits to society.

ANALYSIS OF DATA

The two groups will be compared to verify that no significant differences in group composition were present. The treatment and no treatment groups will then be compared with respect to the occurrence of seizures including their frequency and duration. The treatment and no treatment groups will be compared with respect to the occurrence of levetiracetam side effects or possible side effects. Significance will be determined at p<0.05.

Up to 100 subjects will be recruited for this study. An interim analysis maybe conducted at any time during this study.

References:

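### An optional interim analysis at any time, with one unadjusted p<0.05 and no stated purpose, timing or boundary, leaves the 5% level unguaranteed if its result can be declared significant or stop the trial

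*Combined protocol and SAP*

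**What the plan says.** The whole analysis plan is the short ANALYSIS OF DATA section. Three of its sentences matter here:

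- the threshold: "Significance will be determined at p<0.05";
- the size: "Up to 100 subjects will be recruited for this study";
- the interim: "An interim analysis maybe conducted at any time during this study".

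The groups are to be "compared with respect to the occurrence of seizures including their frequency and duration", and also on side effects. No test is named, and the section does not say which of these comparisons an interim would make. No other section gives a purpose, time, boundary or stopping rule for the interim, or says whether its result may be declared significant. Nothing at this point suggests removed or blacked-out text.

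**The concern.** A final p<0.05 has its usual meaning only if the reader knows whether an earlier look could also have been declared significant. Here the look is optional, its time is open, the threshold is not divided between looks, and recruitment has a ceiling but no fixed end. The Design section adds that patients and caregivers are not blinded, so outcomes by group can be seen as they accrue. Nothing says that the timing of a look would follow those outcomes, and nothing rules it out. At stake is the credibility of any claimed difference, in either direction, from a trial whose Background section says it is meant to settle whether prophylaxis has any utility.

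**Working it through.** **Inputs from the document.** The threshold is 0.05 and the ceiling is 100 (ANALYSIS OF DATA). Half the patients do not get the drug (Risks), so there are 50 per arm at the ceiling.

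**Assumptions, because the plan gives none.** Tests are two-sided (the Hypothesis is of no difference). The outcome is seizure occurrence, tested by uncorrected pooled chi-square or by Fisher's exact test. One interim takes place at 50 patients (25 per arm), at a time fixed in advance. True rates are equal in the two arms and are varied.

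**The plan's own figure.** The only error figure is 0.05, a chosen threshold. One look at |Z|>1.96 gives 5.00%. The plan derives no power or sample size that could be reproduced.

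**Normal approximation.** With one interim at information fraction t and both looks at 0.05, the overall error is 1 − P(|Z1|<1.96, |Z2|<1.96), with correlation √t. This gives 9.5% at t=0.10, 8.3% at t=0.50 and 6.5% at t=0.90.

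**Exact calculation.** Seizures are few, so the approximation is not enough. Let m=25 and n=50 per arm and let π be the common rate. Let A and B be the interim counts, and C and D the later counts from the remaining 25 per arm, all binomial. Then

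error = P[(A,B) rejects at m] + P[(A,B) does not reject at m, and (A+C, B+D) rejects at n].

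Every combination of counts is summed. Results in %:

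| Rate | Chi-square, two looks | Chi-square, final only | Fisher, two looks | Fisher, final only |
|---|---|---|---|---|
| 2% | 1.37 | 1.30 | 0.04 | 0.04 |
| 3% | 3.09 | 2.79 | 0.17 | 0.17 |
| 4% | 4.57 | 3.85 | 0.43 | 0.42 |
| 5% | 5.60 | 4.34 | 0.77 | 0.72 |
| 10% | 8.32 | 5.06 | 2.39 | 1.79 |
| 15% | 9.12 | 5.50 | 3.72 | 2.39 |
| 20% | 8.91 | 5.22 | 4.35 | 2.82 |
| 30% | 8.61 | 4.98 | 4.60 | 3.07 |
| 40% | 9.31 | 5.24 | 5.23 | 3.21 |
| 50% | 10.03 | 5.69 | 5.75 | 3.52 |

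On this schedule chi-square passes 5% between rates of 4.0% (4.57%) and 4.5% (5.14%). Over every single fixed interim from 20 to 98 patients and rates of 1-30%, the maximum is 9.6% for chi-square and 4.9% for Fisher. The 4% row depends on the schedule: with the interim at 76 patients, chi-square reaches 5.03% there.

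**Check of the proposed boundary.** The interim is at 50 patients with p<0.001 and the final test is at p<0.05.

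- Added error over a single final look is at most about 0.02 percentage points, at final sizes of 60, 70, 80, 90 or 100 and rates of 1-30%.
- Power for assumed rates of 20% against 5% is 66.4% (chi-square) or 50.8% (Fisher), with or without the interim.
- Smallest declarable interim difference with no seizures in one arm, chi-square, 0 against 9: the pooled rate is 9/50=0.18, the statistic is 0.36²/(0.18×0.82×2/25)=10.98, and p=0.0009.
- The same with Fisher, 0 against 10: p=2×C(25,10)/C(50,10)=0.0006.

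**The case against.** The harm is conditional three times over. The interim must be able to yield a claim or a stop, which no section says. The test must be one such as uncorrected chi-square, and none is named. The seizure rate must be high enough, and none is given. The Background section says the risk with unruptured aneurysms "appears to be lower in these patients compared with those with ruptured intracranial aneurysms", and such patients are eligible, so low rates are possible. All of this stands. It limits the finding to a level that is not guaranteed. It does not close the gap, because the plan excludes none of these conditions.

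A second objection is that the Hypothesis is one of no difference, so extra chances to reach p<0.05 work against the expected conclusion. The nearer danger would be an early, underpowered look read as showing no difference. This stands in part, and the fix covers it. A false difference in either direction would still mislead.

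A reader might infer two stronger things. One is that following the plan necessarily inflates the error to 8 or 9%. The documents do not support that: with Fisher and one look there is no excess at rates up to 30%, and a safety-only look inflates nothing. The other is that the open timing permits repeated testing. Repeated looks would be worse (41 looks at a 20% rate give 20% with chi-square and 10% with Fisher), but the sentence speaks of one interim analysis. The conclusion does not rest on repeated looks.

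**Conclusion.** The omission is certain; the inflation is conditional. If the single interim may be declared significant or may stop recruitment, the plan does not hold the error at 5%. With uncorrected chi-square, one look at 50 patients and common rates of 5-20%, the error is 5.6-9.1%. With Fisher it stays below 5% at rates up to 30%, and exceeds it only at higher rates (5.2% at 40%, 5.75% at 50%). These figures assume 50 per arm, two-sided tests, a fixed interim time and equal true rates. The point should be fixed: a common test at moderate rates could nearly double the nominal level, and the remedy is cheap.

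**What to change.** Replace the interim sentence with one of the following.

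(a) *Any interim look is for safety only; no between-group significance test of seizure outcomes will be made before the final analysis.*

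(b) *At most one interim between-group comparison will be made, of seizure occurrence only, when outcome data are available for 50 randomised patients, using the test, seizure definition and window fixed in writing beforehand. A difference may be declared, or recruitment stopped for it, only at two-sided p<0.001. Seizure frequency and duration will not be tested for significance at the interim, and side effects will be reviewed for safety without a significance claim. A non-significant interim result will not be reported as showing no difference. Otherwise recruitment continues up to the cap of 100 and the final test is at p<0.05. If recruitment ends earlier for reasons unrelated to between-group results, the final test is made once on all randomised patients and the reason is reported.*

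The cost is a few sentences, the loss of informal looks and, under (b), early claims that will be rare. Safety review stays separate and is not bound by p<0.001.

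Under (b), what remains is the chosen test's own single-look size. At rates of 1-30%, chi-square reaches 5.5% at 100 patients and about 6.0% at 90 (rate 8%). Fisher stays at about 3.1% or less, so it keeps the final test below 5%.

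The investigators must also choose the seizure window, which the final analysis needs anyway. The Design section uses seven days for the drug course and as the discharge point for chart review ("If a subject is discharged prior to 7 days, periodic chart review and examination at routine clinical follow ups"), but also collects seizures at later visits: "These visits typically occur at 1-2 months, 4-6 months, and 6-12 months and up until 5 years +/- 6 months after surgery". With a long window, recruitment may be complete before 50 patients have outcome data, and the stopping clause in (b) would then be idle. Option (a) may be simpler. Neither option justifies 100 as a sample size or supplies a margin for concluding no difference; those are separate matters.
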